3.7 TIMING OF OUTCOME ASSESSMENT

4. STATISTICAL PRINCIPLES

4.1 LEVELS OF CONFIDENCE AND P-VALUES

All confidence intervals presented will be 95% and two-sided.

4.1.1 ADJUSTMENT FOR MULTIPLICITY

n/a

- 4.2 ADHERENCE AND PROTOCOL DEVIATIONS
- 4.2.1 DEFINITION AND ASSESSSMENT OF ADHERENCE

Adherence is defined as attending all seven BCI sessions.

Compliance is assessed based on the percent of subjects who have performed the scheduled number of interventional sessions. It is defined as:

% compliance = (number of sessions performed / number of planned sessions)*100%.

The number of planned sessions in this study is 7.

4 2 2 PRESENTATION OF ADHERENCE

Frequencies table and descriptive statistics of the adherence and "% compliance" will be summarized.

4.2.3 DEFINITION OF PROTOCOL DEVIATION

Physical incapacity to perform the tasks proposed.

4.2.4 PRESENTATION OF PROTOCOL DEVIATIONS

Register of number and type of protocol deviation and number of participants removed. No formal statistical testing will be undertaken.

4.3 ANALYSIS POPULATION

The intention-to-treat population will include all participants irrespective of number of session completed. If required the Centre for Trials Research will investigate methods of analysis that adjust for the number of sessions completed which is preferable to excluding participants which may result in biased results.

5. STUDY POPULATION

5.1 SCREENING DATA

Not applicable.

5.2 ELIGIBILITY

The number of participants eligible and how many were excluded due to violating each inclusion/exclusion criteria will be tabulated.

5.3 RECRUITMENT

A CONSORT flow diagram will be used to summarize the number of patients who were:

- assessed for eligibility
- lost to follow-up*
- discontinued the intervention*.

5.4 WITHDRAWAL/FOLLOW UP

5.4.1 LEVEL OF WITHDRAWAL

The level of withdrawal will be tabulated, considering these aspects:

- Withdrawal from study intervention
- Withdrawal from study follow-up
- Withdrawal from entire study and does not want data to be used.

^{*}reasons will be provided

Short title:	BRAINTRAIN SAP Template

5.4.2 TIMING OF WITHDRAWAL

Timing of withdrawal from follow-up or lost to follow up data will be presented in a table. For each time point information on the number of withdrawals and reasons for withdrawal will be provided.

5.4.3 REASONS FOR WITHDRAWAL

A patient may withdraw or be withdrawn from the intervention for the following reasons:

- Withdrawal of consent for intervention by the participant
- Any alteration in the participants condition or circumstances which justifies the discontinuation of the intervention in the Investigators' opinion.

5.4.4 PRESENTATION OF WITHDRAWAL/LOSS TO FOLLOW-UP

The numbers (with reasons) of losses to follow-up (drop-outs and withdrawals) over the course of the study will be summarised in a table.

5.5 BASELINE PARTICPANT CHARACTERISTICS

5.5.1 LIST OF BASELINE DATA

Measure	Outcomes	Description
Demographic questionnaire	Age, gender, education, SES	
Thought control questionnaire (TCQ)(Wells & Davies, 1994)	Thought control (distraction, punishment, worry; reappraisal; social control)	30-item measure to assess effectiveness of strategies used for the control of unpleasant/unwanted thoughts
Thought control ability questionnaire (TCAQ)(Luciano et al., 2005)	Thought control	25-item measure of individual differences in perceived ability to control unwanted & intrusive thoughts
Wechsler Adult Intelligence Scale (WAIS-III)(Wechsler, 1997)	IQ	Global intelligence/IQ measure

5.5.2 DESCRIPTIVE STATISTICS

Categorical data will be summarised by numbers and percentages. Continuous data will be summarised by mean, standard deviation, minimum and maximum values. Tests of statistical significance will not be undertaken for baseline characteristics.

6. ANALYSIS

6.1 PROGRESSION CRITERIA

Since this study represents a feasibility trial this is not applicable.

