| TCAQ | Thought Control Ability Questionnaire |
| ТМҒ | Trial Master File |
| TMG | Trial Management Group |
| TSC | Trial Steering Committee |

- **USM** Urgent Safety Measure
- VABS Vineland Adaptive Behaviour Scales
- **WAIS-III** Wechsler Adult Intelligence Scale

BCI intervention in ASD V1.0, 24.06.15

1 Amendment History

| Amendment No. | Protocol version no. | Date issued | Author(s) of changes | Details of changes made |
|------------------|----------------------------|----------------|-------------------------|-------------------------|
| | V 1.0 | | | |

2 Synopsis

| Short title | BCI (Brain Computer Interface) Intervention in Autism (BCIAUT) |
|--|---|
| Acronym | BCIAUT |
| Internal ref. no. | IBILI - VB - 2015 – 01 |
| Study design | SINGLE ARM WITHIN – SUBJECT "BEFORE-AFTER" DESIGN. |
| Trial/study participants | ASD (experimental) |
| Planned sample size | 15 (plus 3 in case of drop outs) |
| Follow-up duration | 6 months after last intervention session |
| Planned trial/study | 4 months |
| period | |
| period Primary objective | Increase the number/rate of responses to initiation/response to joint attention cues in a serious game |
| period Primary objective Secondary objectives | Increase the number/rate of responses to initiation/response to joint attention cues in a serious game Improve general social cognition functions |
| period Primary objective Secondary objectives Primary endpoint | Increase the number/rate of responses to initiation/response to joint attention cues in a serious game Improve general social cognition functions Number/rate of responses to initiation/response to joint attention cues |
| period Primary objective Secondary objectives Primary endpoint Secondary endpoints | Increase the number/rate of responses to initiation/response to joint attention cues in a serious game Improve general social cognition functions Number/rate of responses to initiation/response to joint attention cues ATEC, Vineland Scores |

3 Study summary & schema

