5.2 Secondary objectives

Improvements in general aspects of social cognition (as measured by neuropsychological tests) derived from a generalization of the skills learned.

6 Study design

| Patient Information according to eligibility criteria | Intervention - 7 sessions (4 months) Intervention - 7 sessions (4 months) BCI session BCI session C |
|---|---|
| | Image: Signed state sta |

Allocation: not applicable

Endpoint Classification: Efficacy Study

Intervention Model: Single arm

Primary Purpose: Basic Science and clinical feasibility study

Participants: 15 ASD subjects (plus 3 in case of drop outs)

7 Participant selection

The eligible patients for the study should be high functioning ASD adolescents and adults. These participants should also meet all the following inclusion criteria and none of the exclusion criteria. All queries about patient eligibility should be directed to [name] before registration.

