10.5 Adherence

Adherence is defined as attending all seven BCI sessions.

After the enrolment, the participant will be given a schedule with the sessions plan. Additionally, the participant or caregiver will be reminded of each session by telephone-call one week earlier and by message the day before.

On the basis of following the study protocol, follow-up plan should depend on specific situation of participants such as avoiding the holiday or the inconvenient day. When the intervention is over, researchers should remind patients of the next appointment time. For eventual absent participants, researchers should do telephone interviews in time, ask the reason and try to reschedule.

11 Outcome measures

11.1 **Primary outcome measure**

The results [Number of items of social attention that a patient can accurately identify in the avatar's action, e.g. looking at, pointing at] in a separate "Joint-attention task" will be the primary outcome measure. The experimental group will be evaluated in the pre and post evaluation time with this test.

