3. STUDY MATERIALS

3.1 TRIAL DESIGN

A Prospective, Single Arm, Longitudinal Cohort Study to assess improvement social attention in ASD (a BCI approach).

The eligible patients for the study will be subject to the same experience during 4 months and will be evaluated before (session 1) and after intervention (session 7 and follow-up).

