3.3 SAMPLE SIZE

To determine de sample size, we used the G*Power tool (Faul, Erdfelder, Lang & Buchner, 2007):

Test family: t-test;

Statistical test: Means (difference between two different means);

Type of power analysis: A priori; Fixed input parameters: Tail(s): Two;

α err prob: 0.05;

Output: Estimated sample size

		Effe	ect Siz	e dz (ES)
		0.8	0.9	1.0	1.1
	0.7	12	10	9	8
Power	0.8	15	12	10	9
	0.9	19	16	13	11

with
$$ES = Cohen's \ dz = \frac{M_{diff}}{\sqrt{\frac{\sum (x_{diff} - M_{diff})^2}{N-1}}}$$
. Based in other effects described in the literature, the effect

size considered is 0.8 (the means difference is 0.8 standard deviations). In these conditions, for power of 0.8 the estimated sample size is 15.

Without the normality assumption of the distribution of the means differences, we would also need 15 subjects, considering a non-parametric test.

Assuming a 20% dropout rate (based on literature) the sample size will be 18.

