6.2 OUTCOME DEFINITIONS

Criteria	Level	Action
Consent rate	>50%	GO
	30-50%	Potential mitigating strategies
	<30%	STOP
Retention rate	>80%	GO
	50-80%	Potential mitigating strategies
	<50%	STOP
Intervention uptake: % of	>90%	GO
patients in the intervention group	60-90%	Potential mitigating strategies
commencing the intervention	<60%	STOP
Intervention adherence:	>80%	GO
% of attendance rates for patients in the	50%-80%	Potential mitigating strategies
intervention group	<50%	STOP
Acceptability of research	Majority of reports positive	GO
processes and intervention assessed via qualitative interviews	Minor issues identified that can potentially be resolved	Potential mitigating strategies
	Major problems with acceptability reported	STOP
Potential contamination	Majority of reports positive	GO
assessed via qualitative interviews	Minor issues identified that can potentially be resolved	Potential mitigating strategies
	Major problems with contamination reported	STOP

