6.3 ANALYSIS METHODS

6.3.1 LIST OF METHODS AND PRESENTATION

Initially will conduct an exploratory data analysis using graphical techniques (box and scatter plots) and quantitative analysis (statistical measures and frequency table) in order to characterize the sample, detect possible extreme outliers and measurement error.

To detect differences between the three time points of neuropsychological evaluation (session 1, session 7 and follow-up) will perform the Repeated-measures ANOVA. To identify the difference between each evaluation, 95% confidence intervals will be presented. (Note: considering a normal distribution)

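### Does the undefined retention row in SAP 6.2, next to a statement in SAP 6.1 that progression criteria do not apply, leave the feasibility conclusion open to choice after the fact?

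*SAP*

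**What the plan says.** **Progression.** SAP 6.1 disposes of progression criteria in one sentence: "Since this study represents a feasibility trial this is not applicable". SAP 6.2, headed as outcome definitions, opens with a table that gives three bands (GO, possible mitigation, STOP) for six criteria: consent, retention, uptake, adherence, acceptability and contamination.

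**Retention.** The row is labelled only "Retention rate". Its bands are above 80%, 50 to 80%, and below 50%. The uptake and adherence rows say what is being counted; this row does not.

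**Purpose.** Protocol section 6 states: "Primary Purpose: Basic Science and clinical feasibility study". The same list classifies the endpoint as efficacy. The objectives in Protocol section 5 and SAP 2.2 concern joint attention and social cognition, and none is a feasibility measure.

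**Time points.** On the primary outcome, Protocol 11.1 says: "The experimental group will be evaluated in the pre and post evaluation time with this test". SAP 3.1 says participants "will be evaluated before (session 1) and after intervention (session 7 and follow-up". The analysis in SAP 6.3.1 is "To detect differences between the three time points of neuropsychological evaluation (session 1, session 7 and follow-up". The Protocol synopsis places follow-up "6 months after last intervention session".

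**Reporting of losses.** SAP 5.3 plans a CONSORT diagram with losses and discontinuations and their reasons. SAP 5.4.1 separates withdrawal from the intervention from withdrawal from follow-up. SAP 5.4.2 tabulates withdrawals and reasons at each time point, and SAP 5.4.4 summarises losses over the whole study.

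**Numbers.** SAP 3.3 states: "Assuming a 20% dropout rate (based on literature) the sample size will be 18".

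**The concern.** A study with a stated feasibility purpose should fix its feasibility rule before the counts are known. Here one section says progression criteria do not apply and the next prints cut-offs, without saying whether they bind. If they do bind, the retention cut-off can be read at two visits at least six months apart.

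The gap is not covered by another quantitative row. Losses after session 7 cannot affect uptake or session attendance, so retention is the only numerical row that can register them, and it does so only if read at follow-up. Suppose all 18 participants attend all seven sessions and 4 are not seen at follow-up. Uptake and attendance are both 100%. Retention is 18/18 = 100% (GO) at session 7 and 14/18 = 77.8% (middle band) at follow-up. Someone who knew the counts could choose the reading, or decide whether the table applied at all.

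The contamination row adds to the unease, because a single-arm study has no comparator to contaminate.

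**Working it through.** **Where 18 comes from.** For a two-sided paired t-test at alpha 0.05 and effect size dz = 0.8, exact noncentral-t power is 0.821 with 15 pairs and 0.790 with 14. This reproduces the SAP's 15. The enrolled number follows as 15 × 1.2 = 18.

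**Bands with n = 18.**
- GO needs more than 0.80 × 18 = 14.4, so at least 15: 15/18 = 83.3%, 14/18 = 77.8%.
- STOP needs fewer than 9, so 8 or fewer: 8/18 = 44.4%.

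**Chance of GO.** Treat participants as independent, each retained with probability p, so P(GO) = P(Bin(18, p) ≥ 15).

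| p | P(GO) |
|---|---|
| 0.95 | 0.989 |
| 0.90 | 0.902 |
| 0.85 | 0.720 |
| 0.80 | 0.501 |
| 0.76 | 0.341 |
| 0.72 | 0.214 |

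**Chance that the time point changes the label.** Those retained at follow-up are a subset of those retained at session 7. So P(GO at session 7 but not at follow-up) is the difference between two P(GO) values. The documents do not say when the 20% loss occurs, so every split below is an assumption.

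| Assumed pattern of loss | Chance the GO label differs |
|---|---|
| 20% in total, 25% of it by session 7 | 0.989 − 0.501 = 48.8% |
| 20% in total, 50% of it by session 7 | 0.902 − 0.501 = 40.1% |
| 20% in total, 75% of it by session 7 | 0.720 − 0.501 = 21.9% |
| 20% in total, 90% of it by session 7 | 8.8% |
| 20% in total, 95% of it by session 7 | 4.4% |
| 20% in total, all by session 7 | 0% |
| 20% by session 7, then 10% of the rest | 0.501 − 0.214 = 28.7% |
| 20% by session 7, then 5% of the rest | 0.501 − 0.341 = 16.0% |
| 20% by session 7, then 2% of the rest | 6.7% |
| 20% by session 7, then 1% of the rest | 3.4% |
| 10% in total, 25% to 75% of it by session 7 | 9.7% to 5.7% |

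The large values arise because a 20% loss puts expected retention exactly at the 80% cut-off, where one participant decides the label. The Protocol's allowance of 3 drop-outs among 18 leaves 15/18 = 83.3%, which is GO.

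**Chance of STOP.** P(Bin(18, p) ≤ 8) is 0.0009 at p = 0.80 and 0.013 at p = 0.72, the worst case above. The ambiguity is in practice between GO and possible mitigation.

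**What the label feeds.** Neither document describes a follow-on trial that the table would govern, and SAP 6.2 has no rule for combining rows into one verdict. SAP 4.3 includes all participants whatever number of sessions they completed, so the efficacy analysis does not depend on the retention category.

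**The case for a change.** The strongest case for a change is that clinical feasibility is a stated purpose, the mismatch stands in current text, and a few words in the SAP would remove it. Tabulating losses by time point ensures that both counts exist, but does not say in advance which one decides. SAP 3.7, where the timing might have been set out, is a heading without text.

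What stands is that SAP 6.1 and 6.2 do not fit together and that the retention row is undefined. The harm, though, requires a binding decision rule, and the SAP's one direct statement is that progression criteria do not apply. The table also reads like shared consortium text: it speaks of an intervention group and of contamination in a single-arm study, and the SAP's running page text identifies a BRAINTRAIN template. That it is a leftover is an inference, but a reasonable one.

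Bringing the table into force would reverse the SAP's own statement. It would also not fix the outcome by defining retention alone. The consent row has no numerator or denominator either, and the adherence row uses attendance rates while SAP 4.2.1 first defines adherence as attending all seven sessions.

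If an analyst does fill the row in, the natural reading is retention to final follow-up. Session attendance is already covered by adherence, and the SAP's outcome timing consistently includes follow-up. The Protocol sentence cited for the other reading concerns when the primary outcome is measured, not retention.

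**Conclusion.** The observation is accurate, but no change to the plan is needed. The mismatch between SAP 6.1 and 6.2 is clerical, and the missing time point is a detail that analysts can fill sensibly, with retention at both visits recoverable from the planned tables.

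The effect is confined to one row's label. With 18 enrolled, the difference between 15 and 14 retained can move it from GO to possible mitigation. How often the time point would do this ranges from 0% to about 49% across the assumed patterns of loss. That range reflects the chosen splits, independence between participants and, at its upper end, a 20% total loss; it does not come from the documents. The chance of STOP is at most 1.3% in the cases examined.

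No objective, endpoint or later decision rests on the label. The efficacy tests, sample size and safety reporting are unaffected. The conclusion would differ if the sponsor meant the table to govern a decision to proceed, but neither document says so, and SAP 6.1 says the opposite.

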6.2 OUTCOME DEFINITIONS

Criteria	Level	Action
Consent rate	>50%	GO
	30-50%	Potential mitigating strategies
	<30%	STOP
Retention rate	>80%	GO
	50-80%	Potential mitigating strategies
	<50%	STOP
Intervention uptake: % of	>90%	GO
patients in the intervention group	60-90%	Potential mitigating strategies
commencing the intervention	<60%	STOP
Intervention adherence:	>80%	GO
% of attendance rates for patients in the	50%-80%	Potential mitigating strategies
intervention group	<50%	STOP
Acceptability of research	Majority of reports positive	GO
processes and intervention assessed via qualitative interviews	Minor issues identified that can potentially be resolved	Potential mitigating strategies
	Major problems with acceptability reported	STOP
Potential contamination	Majority of reports positive	GO
assessed via qualitative interviews	Minor issues identified that can potentially be resolved	Potential mitigating strategies
	Major problems with contamination reported	STOP

6.2.1 PRIMARY OUTCOME(S)

The results [Number of items of social attention that a patient can accurately identify in the avatar's action, e.g. looking at, pointing at] in a separate "Joint-attention task" will be the primary outcome measure. The experimental group will be evaluated in the pre (session 1) and post intervention (session 7 and follow-up).

6.2.2 TIMING, UNITS AND DERIVATION OF PRIMARY

The experimental group will be evaluated in the pre (session 1) and post intervention (session 7 and follow-up).

6.2.3 LIST OF SECONDARY OUTCOMES

The results in Autism Treatment Evaluation Checklist (ATEC) [Sociability and Cognitive Awareness Subtests] and the results in Vineland Adaptive Behavior Scale (VABS) [Socialization and Daily Living Skills Domains] will be the secondary outcome measures. The group will be evaluated in the pre (session 1) and post intervention (session 7 and follow-up).

6.2.4 ORDER OF TESTING

Not applicable

6.2.5 TIMING, UNITS AND DERVICATION OF SECONDARYS

The experimental group will be evaluated in the pre (session 1) and post intervention (session 7 and follow-up).

6.3 ANALYSIS METHODS

6.3.1 LIST OF METHODS AND PRESENTATION

Initially will conduct an exploratory data analysis using graphical techniques (box and scatter plots) and quantitative analysis (statistical measures and frequency table) in order to characterize the sample, detect possible extreme outliers and measurement error.

To detect differences between the three time points of neuropsychological evaluation (session 1, session 7 and follow-up) will perform the Repeated-measures ANOVA. To identify the difference between each evaluation, 95% confidence intervals will be presented. (Note: considering a normal distribution)

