13.2 Sample size

Considering the longitudinal design proposed, with alpha 0.05, power of 80%, and standardized effect of 0.8 (improvement of 8 points for and estimated SD of 10 points) we would need 15 subjects (plus 3 in case of drop outs). We will add three additional subjects to account for drop-offs. The sample size calculations were performed based on a matched 2 sided paired t-test. To determine these values we used the G*Power tool (Faul et al., 2007). The sample size calculations were performed under the assumption that the distribution of the mean differences is normal. Similarly, without the normality assumption, we would also need 15 subjects, considering a non-parametric Wilcoxon test.

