15.1 Main analysis

A priori, we will analyse the data normality. Considering a normal distribution of the mean differences, the main analysis will consist on a t-test on the means - difference between two dependent means (matched pairs).

The null hypothesis of this test is that the means μ_x , μ_y of pre- and post- intervention, respectively, are identical.

The null hypothesis that $\mu_x = \mu_y$ can be reformulated in terms of the difference $d_i = x_i - y_i$. The null hypothesis is then given by $\mu_d = 0$. The alternative hypothesis states that μ_d has a value different from zero:

 $H_0: \mu_d = 0$

 $\mathsf{H}_{\mathtt{l}}:\mu_{\mathtt{d}} \neq 0$

However, without the normality assumption, we will consider a non-parametric Wilcoxon test.

Further details will be found in the SAP

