3.5 INTERIM ANALYSES

Not applicable.

- 3.5.1 PLANNED SAMPLE SIZE ADJUSTMENT
- 3.5.2 STOPPING RULES
- 3.6 TIMING OF FINAL ANALYSIS

The intervention comprises seven BCI sessions spread over four months. In each session, the subject is asked to identify objects of interest based on the gaze direction of an avatar. Each subject will also undergo neuropsychological evolutions and "Joint-attention task" before the first session, after the last session (short-term) and in follow-up (long-term).

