6.3.4 ALTERNATIVE METHODS IF DISTRIBUTIONAL ASSUMPTIONS NOT MET

Without the normality assumption, we will consider a non-parametric tests: Friedman test and Wilcoxon or Sign test. Since the primary outcome is a count variable it may be more suited to methods that utilize the Poisson distribution. If the primary outcome conforms to a Poisson distribution rather than a normal distribution then Poisson regression will be considered. Effect estimates and 95% confidence intervals will be tabulated.

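### The protocol tests and sizes one paired pre-post contrast, but the SAP never names that contrast as primary and adds follow-up as a second post visit without a decision rule

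*SAP*

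**What the plan says.** **Protocol.** Section 11.1 assesses the primary outcome, the count of social-attention items correctly identified in the Joint-attention task, before and after the intervention. Section 10.3 dates these assessments to week 0 and week 16. Section 15.1 states one null hypothesis, of equal pre and post means, and says that "the main analysis will consist on a t-test on the means - difference between two dependent means (matched pairs", with a Wilcoxon test if normality fails. Section 13.2 sizes the trial on the same test: "The sample size calculations were performed based on a matched 2 sided paired t-test". The 6-month visit in section 12.5 has no hypothesis or test attached.

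**SAP.** Section 3.3 keeps the paired standardised effect of 0.8: "In these conditions, for power of 0.8 the estimated sample size is 15". Section 6.2.1 then widens the primary outcome's time points: "The experimental group will be evaluated in the pre (session 1) and post intervention (session 7 and follow-up". Section 6.3.1 gives one method under normality, the three-visit ANOVA ("To detect differences between the three time points of neuropsychological evaluation (session 1, session 7 and follow-up) will perform the Repeated-measures ANOVA"), and adds: "To identify the difference between each evaluation, 95% confidence intervals will be presented". Section 4.1 makes every interval two-sided 95%. Sections 4.1.1 (multiplicity) and 6.2.4 (order of testing) are marked as not applicable. For non-normal data, section 6.3.4 offers Friedman with Wilcoxon or Sign tests, and raises Poisson regression for the primary outcome: "Since the primary outcome is a count variable it may be more suited to methods that utilize the Poisson distribution".

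**The concern.** The two documents describe different primary analyses. The protocol has one contrast, one test and one fallback. The SAP has three visits, an omnibus test, up to three pairwise intervals and a choice of fallbacks, and does not say which of these settles the primary question. The mismatch also exists inside the SAP, because section 3.3 sizes a paired contrast that sections 6.2 and 6.3 never designate.

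The stated 5% alpha and 80% power belong to the paired test alone. An analyst working from the SAP could report success on session 7, on follow-up, or on the omnibus F, which follow-up alone can make significant. In an unblinded single-arm study, leaving that choice open until the data are seen deprives the stated error rate of its meaning.

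**Working it through.** **1. The plan's own figure.** Inputs from protocol 13.2: mean change 8, SD of change 10, two-sided alpha 0.05. So dz = 8/10 = 0.8. For a paired t-test the noncentrality is dz × √n, and power is the noncentral-t probability beyond the critical value on n − 1 degrees of freedom.

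| n | dz√n | critical t | power |
|---|---|---|---|
| 14 | 2.993 | 2.160 | 79.0% |
| 15 | 3.098 | 2.145 | 82.1% |
| 18 | 3.394 | 2.110 | 89.2% |

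Fifteen is the smallest n that reaches 80%. All 12 cells of the table in SAP 3.3 reproduce. N = 15 is therefore correct for the protocol's test.

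**2. Error rate if the SAP's intervals are read as they stand.** The documents give neither the correlation between visits nor a follow-up mean. Assumed: trivariate normal data, compound symmetry, and SD 10 for every change. Simulation at n = 15 with no effect, 200,000 trials:

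| Rule for declaring success | Chance of a false claim |
|---|---|
| Omnibus F | 5.05% |
| Either 95% interval against session 1 excludes zero | 9.13% |
| Any of the three pairwise intervals excludes zero | 12.50% |
| Any of the three, but only after a significant F | 5.01% |

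A separate run with visit correlations from 0.3 to 0.9 gave 9.1–9.3% for two contrasts and 12.5–12.7% for three. With unequal correlations (0.8, 0.5, 0.8) these were 7.9% and 11.0%, and the uncorrected F-test itself rose to 6.8%. For scale, two independent tests would give 1 − 0.95² = 9.75%.

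**3. Power of the omnibus F.** Under compound symmetry with change SD 10, the ANOVA error variance is 10²/2 = 50. The noncentrality is λ = n × Σ(μⱼ − μ̄)²/50, on 2 and 2(n − 1) degrees of freedom. At n = 15, for means at session 1, session 7 and follow-up:

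| Means | Σ(μⱼ − μ̄)² | λ | F power | Session 7 paired t | F and t disagree |
|---|---|---|---|---|---|
| 0, 8, 8 (gain kept) | 42.67 | 12.8 | 87% | 82% | 11.3% |
| 0, 8, 4 (half kept) | 32 | 9.6 | 75% | 82% | 10.2% |
| 0, 8, 0 (gain lost) | 42.67 | 12.8 | 87% | 82% | 11.4% |
| 0, 0, 8 (follow-up only) | 42.67 | 12.8 | 87% | 5% | 82.0% |

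At n = 18 the first three rows have λ = 15.36, 11.52 and 15.36, F power 93%, 84% and 93%, and disagreement of about 8%. The F-test thus has more power than the paired test in some patterns and less in others. The result turns on a follow-up mean that the plan never states.

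**4. Power if the F-test were a gate.** Requiring a significant F before reading session 7 against session 1 at n = 15 gives about 79%, 74% and 79% for the first three patterns, in a 40,000-trial run. All three are slightly or clearly below the planned 80%. A gate repairs the error rate but not the link to the sample size.

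**The case against.** The strongest reply is that the protocol already settles the matter. Section 15.1 names the main analysis and leaves only further details to the SAP, and the SAP nowhere says that it replaces that test. On this view the SAP merely fails to restate the primary contrast. That is partly right, and it bears on severity. But the SAP does not stay silent: it changes what counts as post for the primary outcome and lists a different method.

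A second reply is that the ANOVA sentence refers to neuropsychological evaluation, which SAP 3.6 lists separately from the Joint-attention task, so the ANOVA may cover secondary outcomes only. The wording is ambiguous. Because section 6.3.4 discusses the primary outcome among the alternatives to that method, the broader reading is the more natural one. On the narrow reading the F-test figures above do not apply to the primary outcome, but the SAP then has no normal-theory method for it at all.

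Third, the 9% and 12.5% depend on a success rule that the SAP does not state. It runs the ANOVA first and the intervals second, which suggests a gate, and SAP 3.6 calls the later visits short-term and long-term, which may be two separate questions. The 12.5% also counts follow-up against session 7, which is not a test of improvement from baseline. These points stand as limits on the figures; they do not supply the missing rule.

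Fourth, this is a small study that both documents describe as feasibility work. Yet protocol section 6 also classifies it as an efficacy study, SAP 3.4 says the main outcomes test superiority, and both documents state a powered sample size. Those statements need a defined test.

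Finally, mean imputation (SAP 6.4) can itself disturb the paired test's error rate. With 3 of 18 post values imputed (an assumption), simulation gave 6.5–7.1%. That is a separate defect and does not affect which contrast is primary.

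**Conclusion.** The concern holds. The contrast that carries the stated alpha and power is not designated in the SAP, and the two documents' analyses can give opposite primary conclusions on the same data. The false-claim rate at n = 15 is about 9% if either comparison with session 1 may count and about 12.5% if any of the three may. It is about 5% if a significant F is required and sphericity holds. No general loss of power is shown, and N = 15 is not in error. The F-test and the session 7 t-test disagree in 10–11% of trials when the planned gain is present at session 7. The 87% against 5% split needs a gain that appears only at follow-up, a pattern the documents do not suggest but the SAP's analysis would accept. All three-visit figures rest on the assumed covariance and follow-up means.

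This should be corrected before analysis because it determines the primary conclusion. A lower grading would be defensible, since the protocol still names the main test.

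**What to change.** - **SAP 6.2.1 and 6.3.1:** name the change from session 1 (before the first session, week 0) to session 7 (after the last session, week 16) on the Joint-attention task as the single primary contrast. Test it with the two-sided paired t-test at 0.05, as in protocol 15.1.
- **SAP 6.3.4:** make the Wilcoxon signed-rank test on that same contrast the only non-normal fallback for the primary outcome. Move Friedman, Sign and Poisson regression out of the primary analysis.
- **Follow-up and the three-visit ANOVA:** label both secondary and state that they cannot support the primary claim. If the ANOVA is kept, add a Greenhouse-Geisser correction.
- **SAP 6.3.1:** say which outcomes the ANOVA covers.

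The sample size of 15 and its power statement then need no change, subject to the separate question of imputation. If the team wants session 7 and follow-up to be co-equal instead, a Bonferroni split at 0.025 each needs 18 evaluable participants; at 15 the power per contrast is 71.7%.

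The cost is SAP wording only, with no change to N, visits or data collection. The one thing given up is that a gain seen only at follow-up could no longer support the primary claim.
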